Household Module. The household section of the questionnaire (answered by the household head or person most knowledgeable about household affairs) will supplement the bari section by providing more detailed information for the two subsampled households. This module will record (i) basic demographic characteristics of all household members (including age, sex, marital status, relationship, education, occupation); the interviewers will only update information in the existing computerized database; (ii) an inventory of household consumption as a proxy for long run income, listing purchases, quantities and prices for foods, personal care and household items and durable goods. For items produced for self-consumption, quantities and source will be detailed--(Note, this submodule will be built on the IRMS questionnaire which takes only 15 minutes to complete) (iii) current household income built up from market wage income, self-employment income and other sources such as share-cropping; (iv) value of household assets (e.g. land, livestock, jewelry, various sentinel items). We will attempt to get information on changes in major household assets since the last census in 1982 where the last asset information was recorded. In addition we will include quality measures (e.g. type of land, value of jewelry) and assign ownership shares where relevant.

Individual income and assets will be collected in subsequent sections of the questionnaire. While individual income will be estimated through questions about employment in subsequent sections of the questionnaire, the household economy questions will focus on the characteristics of household-owned agricultural and non-agricultural businesses. Net returns to family labor, capital, and land, from self-employment activities will be obtained. Since our focus is on income and its sources, not on the production processes themselves, we will not collect detailed data on inputs, which would be very time consuming, particularly for obtaining reliable data on family labor. Instead, we will follow the example of the World Bank's Living Standards Measurement Surveys. For agricultural activities we will collect information by cropping season on the quantities and value of production and inputs--[In terms of a commonly accepted village classification four seasons can be identified: (i) Monsoon-- July-September corresponding to the Aus rice harvest; (ii) Autumn--October-November corresponding to the Aman rice harvest; (iii) Dry Winter--December-February and (iv) Hot dry--March-June]. Non-agricultural net incomes will be collected in a similar way, distinguishing values of production from input expenses by type.

Health Status and Health Care Utilization Module and Physical Performance Module. We intend to measure current health status for adults (all household respondents 15+) using subjective and objective measures as follows (Liang and Whitelaw, 1987; Guralnik et al., 1989): (a) objectively by directly observed measures of physical deficiencies in gait, balance, and strength--Physical Performance Tests; (b) functionally, through self-reported questions about the ability to perform various activities of daily living (ADLs); (c) medically, through questions about the presence of disease symptoms and impairments; and (d) subjectively, through self-assessments. In addition to our experience developing these measures in Indonesia, extensive field testing will be employed to make sure that the questions are culturally and epidemiologically valid in Bangladesh, as well as to establish the appropriate time frame. RAND is well-equipped based on its experience with the Malaysian, Indonesian and domestic surveys to develop and validate subjective measures of health and functioning. In his field test of a modified IFLS questionnaire with elderly (60+) respondents in Matlab, [name] found that the basic protocol for ADLs implemented in RAND's Indonesian

projects adapts well to Bangladesh. The MFLS-2 included activities of daily living and self-assessment questions for physical health that were adapted to the Malaysian context, and both the IRMS and IFLS included extensive questions about health, well-being and absence from daily activities. RAND's experience is built on the Medical Outcome Study (Stewart et al., 1988), which developed and clinically validated a standard set of questions for measures of physical and mental health which have been adapted in many contexts. In addition, we will use non-overlapping questions from the WHO and ASEAN surveys to expand the universe of potential questions. [name] is using these instruments in his smaller-scale survey of the elderly; this experience will contribute significantly to the MHSS.

To supplement self-assessment and ADL questions for sample household seniors and prime age adults, we will conduct objective observational tests of respondents' gait, balance and strength using protocols designed as part of the WHO's international protocol for creating "objective, directly measured" tests of functional disability as a determinant of healthy aging. Interviewers will be trained in a highly structured protocol which allows them to measure respondents' ability to complete a variety of physical functioning exercises, including side-by-side, semi-tandem and tandem stands, measured walks, standing from chair sitting, functional reach and vision. The protocols, developed by the Demography and Biometry Program of the National Institute on Aging and used in the National Health and Nutrition and Examination Survey, round III (NHANES III), instruct the interviewer in determining the advisability of administering the exercise (for impaired respondents), provide a scripted set of instructions for the respondent, and detail the measurement techniques and equipment necessary to provide accurate data. The NHANES III protocol consists of a 7 items scale which has good construct validity, reproducibility and reliability (Cronbach's $\alpha > 0.85$). The only equipment required is a chair-height cube, tape measure and a stopwatch. Modifications of this protocol have been piloted on the elderly in a number of countries in the developing world (China, Sri Lanka, Bahrain) and moreover have been tried out under the sponsorship of WHO on prime age adults in China.

In addition to health status measures, a number of indicators of curative and preventive health care utilization will be asked. These include from whom and from where medical care was received (including self-treatment, traditional and modern providers), how much it cost, how far the respondent traveled, and whether drugs were purchased. Again, the most problematic point will be the recall period and the ability to tie curative health utilization to previous episodes of illness. In Indonesia we have successfully used a four week reference period for acute illnesses and a one year reference period for utilization, and [name] successfully pretested recall of symptoms questions using a four-week recall period in Matlab in 1991. In Matlab we will place special emphasis on home delivery because of the MCH-FP program.

Life History. The most detailed section of the questionnaire will be devoted to detailed current and retrospective questions to be administered to all household respondents age 15 and older in the two selected households. These questions will focus on marriages and unions, education, labor force participation, migration, individual assets and transfers, and the characteristics and living arrangements of non-coresident family members.

Marriages and unions. We will work from the DSS data on marriage history to obtain detailed histories of respondents' unions, including characteristics of former or non-coresident spouses, dowries and bride prices, marriage arrangements, relationship prior to marriage, number of children produced and living from unions, current relationships with former spouses, and assets at the time of a union-terminating event.

Schooling, training and labor force participation. Respondents will be asked to give complete retrospective accounts of their education and job training, occupations, weeks worked and usual weekly hours of work, earnings, and distance to work (for both primary and secondary jobs). In order to include female respondents, 'work' will be defined broadly to include both formal and informal sector, full-time and part-time, and seasonal (during major rice harvests) and year-round activities. This complete work history will begin at age 15 (or age of marriage, whichever is earlier), and go to the time of the interview with varying levels of detail. Major changes of occupation will be asked in 5 year intervals and will also be keyed to migration data. Time allocation for the past week's main income generating activities will be collected for all adult household members.

Migration. As part of the life history, the survey will determine the extent of geographic mobility of individuals and families, and ascertain the causes and consequences of families' migratory movements, including short-stay and circulatory migration. Again, the DSS data provide quite complete migration records with dates of in- and out-migrations for the household and basic descriptors of the reasons for migration and destination- (Note in terms of the Matlab computerized database, only migration durations greater than six months are counted). The instrument will expand on these data, focusing on the motivation for moving, distance moved, economic support received before and after moving, and employment status after moving.

Financial status. Information on current incomes from all sources and assets for all adults will be obtained by asking detailed questions about market labor earnings (including in-kind payments and fringe benefits) and time worked. Income from gifts and other transfers will be collected, distinguishing categories such as land rental, pensions, support from relatives (cataloging the exact relationship and location of the giver), inheritances, and dowries or wedding gifts. These data were also obtained in both Malaysian surveys and in Indonesia, and in Matlab will be repeated with a special focus on the financial status of elderly household members. Also in Matlab, the questionnaire will emphasize detailed information on inter-generational resource transfers both within the sample bari and from outside of the bari. Transfers of both cash and goods and services will be collected by source and tied to specific events (e.g., illness, education). The characteristics of individuals who could potentially provide time or monetary support (as well as those who did) will be collected so that a measure of the complete transfer choice set is created. In addition, we will measure transfers out to allow for measure of net transfers to the household.

Characteristics of non-coresident immediate family. Detailed information on the location and socio-demographic characteristics of non-coresident (i.e., outside the household) immediate kin (parents, siblings and children) will be collected. The primary purpose of these questions will be to provide information on social support networks for household members, particularly the elderly. The socio-demographic characteristics of non-coresident family members (age, sex, relationship, educational attainment, health status, occupation, and ages at death if dead) will be collected in addition to frequency and nature of contact. In addition, these questions will provide further information to allow tracking of recent out-migrants.

Fertility Questionnaire. Contrary to the conventional procedure for selecting female respondents 15-49 for fertility and family planning questions, we intend to interview all female respondents 15+ in the two selected households. By focusing on all 15+ females rather than the 15-49 group, we will be able to investigate the cumulative effect of pregnancies on women's health over the life cycle and particularly at older ages. The Matlab DSS records provide detailed data on dates and outcomes of live birth pregnancies for all ever married women in the treatment and comparison area since 1974. In addition to the DSS, the RKS data provide information on menstrual, lactation and contraception status on a month by month basis for the treatment area women since 1978. Our goal is not to duplicate these data but to provide recall of pregnancy events not in the Matlab computerized database, and to provide more detailed recall of certain events. Interviewers will enter households with pre-printed pregnancy records from the DSS/RKS databases. Each respondent will be asked about outcome, sex of the child, contraceptive use, duration of postpartum amenorrhea, the practice of postpartum abstinence, and ages at menarche and menopause.

We note the unusual opportunity to compare these newly collected data to the longitudinal record-keeping of the RKS/DSS record keeping systems. In a pretest, a subsample of ever-married female respondents in the comparison and treatment areas will be administered the retrospective questionnaire without reference to the existing longitudinal Matlab database. This will allow us to judge how use of the existing data enhances recall and to estimate the rate of recall decay without the existing Matlab data in this domain.

Characteristics of children and child health and survival. All household members 15+ will be asked to report by proxy on characteristics of their ever born children, regardless of survival and co-residence. If the respondent is male and has a spouse present, the spouse will answer for the children belonging to the couple. Otherwise the father or "best guardian" (usually older sibling, aunt etc) will respond. Respondents will be asked about:

- o Socio-demographic characteristics: age, sex, birth order, approximate size and weight at birth, ages of

- parents at time of birth of child, educational attainment, occupation, location and frequency of contact for non-co-resident children, and for dead children, age of child and age of both parents at time of death;
- o Morbidity (only for currently alive children 0-14 years): short-term recall of diarrhea, respiratory infections, measles plus long-term recall of neonatal tetanus;
 - o Health care utilization (only for currently alive children 0-14): antenatal care and birth attendance; immunizations; participation in village health and nutrition programs; treatment of diarrhea; attendance at hospitals, clinics, or health posts; use of private or traditional health care.

Anthropometrics. A separate data recording card will be issued to measurement specialists to record anthropometric data. The measurement specialist will collect data on all household respondents - infants, children, adults and the elderly - on height and weight following accepted international standards (United Nations, 1986). We will use trained female anthropometrists for the most part and will make sure that all measurements are validated and weighing scales calibrated regularly. Furthermore anthropometrists will be checked for bias, precision and accuracy--it is worth noting that ICDDR,B has extensive institutional experience in collecting anthropometric information. [name] (from Cornell University) and [name] (from ICDDR,B) two internationally known experts on anthropometrics will be consulted on these measurement protocols.

These weight and height measures enable us to study an age-independent measure of nutritional status. Weight-for-height is a standard measure of children's acute nutritional status. When measuring heights in field conditions, it is usual to measure recumbent length for children under two years old, and height for children older than two and for adults. For children under two years the most common way to take weights is to use Salter scales, which can be hung from structures such as trees; in Matlab, however, we plan to use an electronic (Seca) scale in which the child is placed in a bassinet. The electronic scale is easier for the measurer, less intimidating to the child and accurate to a higher precision.

Given our within household sampling scheme we will be measuring anthropometric data for child sibling pairs and parent child pairs. This will allow us to examine family level heterogeneity in health status for parent-child and sibling-sibling relationships, and may provide some sense of the household disease environment. For example, recent studies have established the usefulness of controlling for parental heights when examining the determinants of children's heights or weight to height, partly to control for genetic factors and partly to control for unobserved family background characteristics (see Thomas, Strauss, and Henriques, forthcoming).

Cognitive Ability. We will assess cognitive ability for all household respondents age 6+ on two dimensions, intellectual capacity/cognitive sophistication, and level of intellectual skills necessary to daily functioning. The cognitive sophistication test will take the form of a culturally-neutral, nonverbal test such as Raven's Progressive Matrices tests or another image-based test. These types of tests can only be interpreted normatively, however normative scores for different age groups are available for Raven's tests and similar tests are widely available. Of particular relevance is the experience with Raven's tests which have been successfully administered in a number of developing countries and particularly in Pakistan, in many ways a culturally similar population. In order to get more objective measures, we also will present some basic verbal and quantitative exercises that center on activities necessary for daily living, such as making change, treating diarrhea with home made oral rehydration solutions. We will adapt a test used by the Bangladesh Rural Advancement Committee (BRAC) which measures levels of knowledge, literacy, comprehension and basic math. Its advantages are that it does not require literacy to complete, it has been thoroughly tested for 11-12 year olds in Bangladesh and successfully administered to children 8+, and given low levels of schooling in Bangladesh, it can be easily adapted to the testing of adults. A particular advantage of these types of functioning tests are that they can be used as baselines for children for later data collection.

Physical Activity and 24 hour diet recall: In order to assess cross-sectional variation by socio-economic status in women's adaptive responses to the nutritional and health stresses of pregnancy and lactation, all female household respondents 15-49 will be interviewed about their physical activity in the week prior to the interview and their diet in the 24 hrs prior to the interview.

For the physical activity module, we will modify appropriately protocols used in the IFLS and the Cebu

Longitudinal Health and Nutritional Study surveys. We will measure allocation of time during the past week in various tasks: main and secondary jobs, home-based income generating activities and work around the house. A list of activities will be generated from pre-tests and focus groups. In addition we will explore the literature for use of measures on posture and activity specific energy expenditures.

For the 24 hr dietary recall, we will adapt the protocol used in the Cebu Longitudinal Health and Nutritional study. We will record information on timing of meals, names of dishes, amounts, preparation method/location, amounts of ingredients. Pretests will determine a common list of dishes (and those proscribed during pregnancy), common measures of quantities and common ingredients.

Community Questionnaire. Along with the household/bari sample described above, we also plan to survey 500 facilities / providers (including, schools, health and family planning clinics, and individual health/family planning practitioners) serving the Matlab surveillance population. Our primary objective is to obtain information on the quality of facilities/providers and their impact on health and educational outcomes and service utilization for the household respondents in the primary sample. Our survey will result in a census of all educational, health, and family planning institutions of any significant size and a select sample of individual health and family planning providers, both modern and traditional, including those who provide services in the home (as in the ICDDR,B program). **The set of facilities/providers to be surveyed will be drawn from a list of facilities/providers that household respondents (in the primary sample) claim to know about, regardless of actual use. The important thing to note is that we are establishing the characteristics of facilities/providers in the opportunity set of our primary sample household respondents and not just those they mention having used (an important bias in several previous community surveys).** In addition to the facility/provider component of this community survey we will also collect community level information on water supply and sanitation, transportation, basic infrastructure, economic activities and food supply and prices from knowledgeable individual (village elders, government officials). Where possible, we will attempt to merge in existing secondary datasets to provide infra-structural information, including information on Matlab project facilities.

During the fieldwork, specially designated interviewers will approach knowledgeable persons in the community (such as the school principals, and clinic administrators) to collect the following data:

- o The number, type, location, staffing, and service hours of family planning clinics and health clinics serving the community, methods and services available and their prices, typical waiting times, and when clinics were established or expanded. Similar information will be obtained for private practitioners and traditional healers.
- o The number of private outlets in the community where contraceptives and medicines are sold, prices, and approximate volume of sales by product.

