- * As noted above, within the bari we will select up to two households. For baris with two or fewer households, all households will be chosen. For baris with greater than two households, the first household will be chosen at random; the second household will be selected from the bari in order of preference as follows: (i) The household of the father and/or mother of the head of the first sampled household (ii) A randomly chosen household containing a brother of the head of the first sampled household (iii) A randomly chosen household containing a son of the head of the first sampled household (iv) A second randomly selected household.
- * Once the two households in the bari are selected, respondents within each household will be chosen in three age strata. (i) All household members 50 years and above will be chosen as respondents. (ii) From the pool of household members aged 15-49, if there are two or less we will pick all. If there are more

than two, the following strategy will be employed: If an individual is the household head or the wife of an household head, then that individual will always be chosen. In addition to the household head and or spouse, another individual 15-49 will be chosen at random along with their spouse if present. At this stage if we have two 15-49 year old respondents we will stop. However if we have only one respondent in the 15-49 age group and there are other 15-49 year old individuals in the household, we will pick another at random along with their spouse if present. (This will lead to a maximum of 4 adult respondents in the 15-49 age group); (iii) Among the pool of children in the household aged 0-14 years, all those sharing a parent will be pooled together in the same sibling group. Only sibling groups whose parent has been selected in rounds 1 or 2 above are eligible for selection as child respondents. From those eligible, one sibling group will be chosen at random and from within that group upto two siblings will be chosen. If that group has only one child, then another sibling group from the eligible pool will be chosen. Here again upto two siblings will be chosen. (This will lead to a maximum of 3 child respondents aged 0-14 years).

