The probability of selecting a particular adult given that their household was selected is a similar calculation to the household sampling probability calculation. We need to enumerate all of the ways that a particular adult could be sampled. These are either through sampling with certainty, random sampling from a stratum, or through the kinship rules. The overall probability that a household will be selected can then be calculated from the conditional probabilities of the various ways that the household could be sampled. In summary, the probability of selecting any given adult is $p(\text{selecting the bari}) * p(\text{selecting the household given the bari is selected}) * p(\text{probability of selecting the adult given that the household is selected})$. Weights for individual adult level analysis are proportional to the reciprocal of this probability.

Sampling probabilities for the children is a similar calculation to the adult calculation although a bit simpler due to the simpler sampling rules. Given the selection of a sibling group, the probability that a particular child is chosen is inversely proportional the number of siblings in the group. The only complication is the possibility that a child is sampled in a second stage because the first sibling group only had one child. These probabilities can be calculated from information on the roster. In summary, the probability of selecting any given child is $p(\text{selecting the bari}) * p(\text{selecting the household given the bari is selected}) * p(\text{probability of selecting the adult given that the household is selected}) * p(\text{selecting the child given that the child's adult was selected})$. Weights for individual child level analysis are proportional to the reciprocal of this probability.

Every member of the bari has a well described and non-zero probability of being sampled. The probabilities are a bit difficult to work out due to the importance of the family structures and interconnections. This is, however, an unavoidable consequence of the importance of collecting data that will inform the effects of family relationships on the outcomes of interest.

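### The stated child selection probability is wrong for one-child sibling groups; applied literally, it halves their weight relative to all other children

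*Protocol*

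**What the plan says.** The selection rule is in Protocol section D, Sample Design, in the list of key features for the primary sample. Children aged 0-14 are pooled into sibling groups, and a group is eligible when a parent has been selected. Then: "From those eligible, one sibling group will be chosen at random and from within that group upto two siblings will be chosen". For a group of one: "If that group has only one child, then another sibling group from the eligible pool will be chosen", followed by "Here again upto two siblings will be chosen". The stated result is: "This will lead to a maximum of 3 child respondents aged 0-14 years".

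The weighting rule is in the same section, under Properties of Sample Design, in the paragraphs on weights for units below the bari. Given that a sibling group is selected, it says that "the probability that a particular child is chosen is inversely proportional the number of siblings in the group". It allows one exception: "The only complication is the possibility that a child is sampled in a second stage because the first sibling group only had one child". It adds that the roster holds what is needed to work out the probabilities, and ends: "Weights for individual child level analysis are proportional to the reciprocal of this probability".

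**The concern.** The two places describe the same step, the choice of a child within a group already drawn, and they give different probabilities. Taking up to two children means that groups of one and groups of two are both taken whole, so their children have the same probability at this step. The weighting text makes the first probability twice the second.

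The weights are reciprocals of these probabilities, so the discrepancy would carry straight into every weighted child-level estimate. Children are 7463 of the 21,798 expected primary-sample respondents (11,077 + 10,721), about a third. Project 4 depends on their anthropometric, cognitive and schooling data. The same within-household scheme is used for the DNFS and outmigrant samples, and the data are meant for public release, so outside users could inherit the weights.

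**Working it through.** **Inputs.** From the selection rule: two children are taken from a selected group, or one if it has only one; after a one-child group, one further group is drawn and again up to two are taken. From the weighting text: probability c/n for some constant c, and weight equal to 1/probability. Here n is the number of siblings aged 0-14 in the group.

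**The protocol's own figure.** The maximum of three child respondents reproduces: 1 from a one-child group plus 2 from the second group. The c/n rule does not reproduce for all n.

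**Step 1: within-group probability.** Under the selection rule, P(child | group selected) = min(1, 2/n). The weight factor is its reciprocal, max(1, n/2).

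| n | Selection rule: P | Correct weight factor | Weight factor under 1/n |
|---|---|---|---|
| 1 | 1 | 1 | 1 |
| 2 | 1 | 1 | 2 |
| 3 | 2/3 | 1.5 | 3 |
| 4 | 1/2 | 2 | 4 |
| 5 | 2/5 | 2.5 | 5 |
| 6 | 1/3 | 3 | 6 |

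With c = 2 the stated rule is exact for n of 2 or more but gives a probability of 2 at n = 1, which is impossible. With c = 1 it is right at n = 1 and gives half the true probability everywhere else. No constant works throughout.

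**Step 2: relative weight.** For a child in a one-child group against a child in a group of n (n at least 2), the correct ratio is 1/(n/2) = 2/n. The stated rule gives 1/n. The second divided by the first is 1/2 for every n.

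**Step 3: does the second draw repair this?** Take a household in which the listed groups are all eligible, and handle both draws exactly.

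- Groups of 1 and 2. The one-child group is drawn with probability 1/2. The two-child group is drawn with probability 1/2 + 1/2 = 1, because it always follows if the other comes first. Correct child probabilities are 1/2 and 1, so the relative weight is 2. With 1/n inside the group they are 1/2 and 1/2, so it is 1.
- Groups of 1 and 3. Correct: 1/2 and 2/3, relative weight 4/3. Stated rule: 1/2 and 1/3, relative weight 2/3.
- Groups of 1, 1 and 4. Group probabilities are 1/2, 1/2 and 2/3. Relative weight of a child in a one-child group against one in the group of four: correct 2/3, stated rule 1/3.
- Groups of 2 and 3. Relative weight is 2/3 under both rules.

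The factor of one half survives correct handling of the second draw. That draw changes the group's probability, not the child's probability once the group is drawn. The last example confirms that groups of two or more keep correct relative weights.

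**Step 4: effect on estimates.** The protocol does not give the share s of children who are in one-child groups, so s is assumed. Halving their relative weight turns s into 0.5s/(0.5s + 1 - s). The shift in a mean is (s minus the new share) times the difference between the two kinds of group, here assumed to be 0.3 SD.

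| Assumed true share | Share under the stated rule | Shift in a mean |
|---|---|---|
| 10% | 0.05/0.95 = 5.3% | 0.014 SD |
| 20% | 0.10/0.90 = 11.1% | 0.027 SD |
| 30% | 0.15/0.85 = 17.6% | 0.037 SD |

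**The case against.** The strongest reply is that the sentence is a prose summary and that the operative instruction is to take the reciprocal of the actual selection probability, worked out from the roster. The sentence names no constant. A programmer who goes back to the selection rule will use 2/n, meet a probability of 2 at n = 1, cap it at 1 and get the right weights. That stands as far as it goes: the error arises only on literal application. It does not remove the point. The sentence sits in the text that defines the weights, and calling the second draw the only complication leaves no room for the exception that is needed.

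A second reply is that 1/n would be exact if one child were taken per group, and the description in the funder's site-visit report does speak of one child. The current design does not. It allows up to three, and its expected 7463 children in 5000 households is 1.49 per household.

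Three stronger readings are tempting, and the documents do not support them.

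- A reader might infer that children in one-child groups are mostly first-born and young, so that the direction of bias is known. Groups are formed only from children aged 0-14 in the household, so a lone child may equally be the youngest, with siblings over 14 or gone. The direction is unknown.
- A reader might infer that a separate factor is needed because either parent can make a child eligible. The selection rule takes the head and wife, everyone aged 50 and over, and the spouse of any randomly chosen adult. Co-resident parents therefore usually enter together, and the difference is confined to narrow cases such as a non-head couple on either side of age 50. A simple extra multiplier would not be exact either, since the number of competing groups depends on which other adults are drawn.
- A reader might infer that the child weights as a whole are unsound. Only the comparison of one-child groups with all others is affected.

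**Conclusion.** The sentence is wrong as written. Under the protocol's own selection rule the within-group probability is min(1, 2/n), which is inversely proportional to n only from n = 2 upwards. If the sentence is followed literally, children in one-child groups carry exactly half their correct weight relative to children in larger groups. That factor rests on the protocol text alone.

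The effect on estimates is modest and rests on assumptions: about 0.01 to 0.04 SD for true shares of 10 to 30% and a 0.3 SD contrast, none of which the protocol supplies. Adult, household and bari weights are untouched, and correct child weights remain recoverable from the roster. It should be corrected because the rule is explicit, the weights may be passed on to other users, and the correction is cheap.

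**What to change.** In the paragraph on child weights, replace the sentence with wording such as: *Once a sibling group has been drawn, each child in it has selection probability min(1, 2/n), where n is the number of siblings aged 0-14 in that group.*

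Add that the group's own selection probability is to be computed from the roster by enumerating the possible adult selections in the household and, for each, the second draw that follows a one-child group. This covers eligibility through either parent without a separate multiplier.

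A simple check on any weighting program is that the within-group factor should be equal for groups of one and groups of two.

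The text change is a sentence or two. The enumeration takes some programming, but reciprocal-probability weights already call for it. Sample selection, fieldwork and questionnaires stay as they are.
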